9.3 Criteria for individual subject withdrawal

A subject *must* permanently discontinue study drug treatment for any of the following reasons:

1. The subject becomes pregnant (pregnancy test will be performed for female patients with child bearing potential during each visit). If a patient becomes pregnant, treatment must be *immediately* discontinued. The pregnancy must be reported to the NIB (treating physician/research nurse) and to the IRB immediately. Information about the subject, the subject's pregnancy, the outcome of the pregnancy, and the status of the infant at 8 to 12 weeks of age will also be collected.
2. The subject desires to discontinue study drug treatment under this protocol. Patients have the right to withdraw from the study at any time and for any reason. The investigator also has the right to withdraw patients from the study in the event of an intercurrent illness, adverse events, treatment failure, protocol violations, administrative reasons, or other reasons.
3. 1st MS safety criterion: Worsening of more than two points on the EDSS scale (*Kurtzke 1983*) compared to baseline, confirmed one month later on an extra follow-up visit. The treatment will be discontinued, but the patient will be followed off therapy to collect all predetermined outcome measures as per "intention to treat" analysis.
4. 2nd MS safety criterion: The average number of new CEL (which represents a measure of MS-related brain inflammatory activity) increases after initiation of idebenone therapy 3 standard deviations above the average number of CEL during pre-treatment baseline and IPPoMS trial or for patients with no CEL observed on MRIs collected during baseline period (expected to be the majority of PP-MS patients), the number of CEL recorded on a

single follow-up MRI reaches 10 CEL (total). Treatment will be discontinued, but the patient will be followed off therapy to collect all predetermined outcome measures as per “intention to treat” analysis.

5. Laboratory safety criteria: ALT (SGPT) or AST (SGOT) more than three times the upper limit of normal during regular laboratory monitoring and remains more than three times the upper limit after one week of cessation of idebenone dosing. Any other highly abnormal laboratory finding that is deemed critical by an investigator and that persists for 1 week after cessation of drug dosing.

The reasons for discontinuation of the study drug must be recorded in the subject’s Clinical Center patient file. Patients discontinuing dosing will be followed for an additional 2 months. If discontinuation was because of an adverse event, the patient will be followed until the event is resolved or stabilized. If the discontinuation was because of pregnancy, the subject will be followed until after the birth.

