3. PRECIS

3.1 Objective:

A Phase I/II clinical trial is being conducted to investigate the safety, therapeutic efficacy and mechanism of action of idebenone in primary-progressive multiple sclerosis (PP-MS) patients (IPPoMS (Protocol Number 09-N-0197)). Patients who have completed the 2-year treatment period of IPPoMS, may enter into this open-label extension study (IPPoMS-E) if they are found to be eligible by the Investigator and desire treatment with idebenone despite remaining blinded as to their allocation to active treatment versus placebo during the IPPoMS trial. The aim of this open-label extension study is gather additional data on safety, efficacy and effects of idebenone on CSF biomarkers in these patients over a period of 1 year. This study will provide open-label idebenone for patients with PP-MS, previously randomized to idebenone or to placebo in the blinded phase of IPPoMS.

3.2 Study Population:

Patients who were previously enrolled in the IPPoMS (Protocol Number 09-N-0197) will be invited to participate in the trial. The same idebenone dose used in the randomized clinical trial (2250 mg/day) will be used in this study.

3.3 Design:

This is a single group, open-label safety and efficacy extension trial with a one year treatment period. Patient-specific biomarkers of disease progression, CSF biomarkers of oxidative stress, longitudinal neuroimaging including quantitative measures of CNS tissue destruction and clinical data will be collected as in the randomized study.

3.4 Outcome Measures:

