The measurement and collection of data will be performed as in the randomized trial. Quantitative neuroimaging measures of central nervous system (CNS: i.e. brain and spinal cord) tissue destruction and clinical and functional measures of neurological disability will be collected every 6-12 months. Additionally, biomarkers focusing on analysis of reactive oxygen species (ROS) and oxidative stress will be collected every 12 months. The primary outcome measure defined in the IPPoMS trial will be also utilized in IPPoMS-E. For patients originally randomized to placebo, patient-specific slopes of disease progression during 2 years of placebo therapy (as measured by primary and secondary outcomes) will be compared to patient-specific slopes of disease progression during 1 year of open label idebenone therapy. Combination of IPPoMS and IPPoMS-E trials will significantly expand paired “no therapy” vs. “idebenone therapy” CSF samples for biomarker studies. It will also provide (for the subgroup of subjects who were originally randomized to idebenone) longitudinal CSF samples on idebenone therapy (collected 2 years apart). This will allow calculations of intra-individual changes in CSF biomarkers on and off idebenone therapy, which may provide important insight into the mechanism of action of idebenone in PP-MS.

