11.3 Handling of missing/unobtainable data

All efforts will be made to collect a complete set of data by employing 2-4 week flexibility in scheduling and repeating inadequate quality MRI scans.

In the event that particular data points are missing for reasons other than inability to perform the test (i.e. because of disability) we will replace the missing data according to following algorithm:

- a. For data obtained every 6 months (i.e. clinical data and brain MRI data), the missing time point will be substituted by the average of 2 adjacent time-points: i.e. 6 months before and 6 months after the missing time-point. If the last time-point is missing (i.e. month 36), we will substitute the data for this time-point by the average of 2 preceding time-points.
- b. For data obtained once at treatment phase (i.e. CSF and apheresis data), the missing data cannot be replaced and the patient will be eliminated from analysis.

Handling data missing because the patient was unable to perform the test due to disability: this may happen for clinical tests such as timed 25 foot walk (25FW), 9 hole peg test (9HPT) and PASAT. These data will be calculated using the following recommendations from scoring instructions for the MSFC:

- a. 25FW: the inability to perform 25FW will be substituted by the largest Z-score in the MSFC Task force database (i.e. with the slowest time of any patient in the combined dataset used by the Task Force in its published meta-analysis). The largest Z-score in the

Task Force dataset is 13.7, therefore, for a subject who could not complete the 25FW Z_{leg} , average = -13.7 will be used.

- b. 9HPT: the inability to perform 9HPT will be coded as 777 and the following Z-score calculation formula will be applied:

$$Z_{arm, trial\#} = [(1/777 - \text{Baseline mean (1/9HPT)}) / \text{Baseline SD (1/9HPT)}]$$

- c. PASAT: In the event an individual patient cannot complete PASAT-3 due to disability, a score of 0 will be assigned.

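### Section 9.3 item 2 lets a worsening patient be withdrawn from the study, against the full follow-up in items 3 and 4, and could bias slope or change comparisons towards idebenone

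*Combined protocol and SAP*

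**What the plan says.** Section 9.3 contains three rules on what happens to outcome data when a patient does badly.

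- **Item 2:** "The investigator also has the right to withdraw patients from the study in the event of an intercurrent illness, adverse events, treatment failure, protocol violations". The sentence goes on to administrative and other reasons. Treatment failure has no definition or threshold in 9.3 or elsewhere, and no later outcome collection is required.
- **Items 3 and 4:** for the two MS safety criteria, item 3 reads "The treatment will be discontinued, but the patient will be followed off therapy to collect all predetermined outcome measures as per" intention to treat, and item 4 says the same in substance. The item 3 trigger is "Worsening of more than two points on the EDSS scale", confirmed a month later. Item 4 is triggered by contrast-enhancing lesions.
- **Closing paragraph:** "Patients discontinuing dosing will be followed for an additional 2 months", with longer follow-up only for adverse events and pregnancy.

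The design (section 3.3) is: "This is a single group, open-label safety and efficacy extension trial with a one year treatment period". For patients from the placebo arm, section 3.4 has off-drug slopes "compared to patient-specific slopes of disease progression during 1 year of open label idebenone therapy". Section 10.2.1 words most imaging outcomes as individualized rates. Sections 10.2.2 and 11.2 use an AUC normalised to one year, without saying whether it is taken on the raw level or on change from the start of the period.

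For clinical and brain MRI data, section 11.3(a) states: "If the last time-point is missing (i.e. month 36), we will substitute the data for this time-point by the average of 2 preceding time-points". Under 11.3(b), a patient with a missing CSF or apheresis value is left out of that analysis. Section 11 defines no analysis population and no rule for patients withdrawn for failure.

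**The concern.** In a progressive disease, treatment failure is the efficacy outcome seen from the clinic. A right to end a patient's participation for that reason therefore permits loss of data that depends on the outcome. Items 3 and 4 show that the authors wanted worsening patients kept in data collection, but they protect only confirmed EDSS worsening of more than two points and the lesion criterion. A patient who worsens less on EDSS, or only on the walk, peg test, MSFC or Scripps scale, has no such protection if the investigator uses item 2.

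The loss is one-sided. Off-drug values from the parent trial are already recorded, so withdrawal can shorten only the open-label year. When month 36 is then filled with the mean of months 24 and 30, a worsening patient receives a value below the one already observed at month 30. What is at stake is the within-patient comparison of progression off and on drug, which has no concurrent control to expose the loss.

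**Working it through.** **1. The rules side by side.** Item 2 speaks of leaving the study; items 3 and 4 speak of stopping treatment and continuing assessment. If item 2 is read as stopping drug only, the two-month rule applies. Clinic visits after baseline fall at months 30 and 36, so two months of follow-up does not secure month 36 for a patient who stops at month 30. If a patient leaves before month 30, 11.3(a) gives no workable value, because filling month 30 needs month 36 and filling month 36 needs month 30.

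**2. Inputs.** There is no plan figure to reproduce: section 11.4 declines a power calculation, and no SD, effect size or withdrawal rate is given. The following are assumptions:

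- inert drug, linear mean worsening of 1 unit per year (higher is worse);
- between-patient slope SD 0.5-1.0, visit noise SD 0.25-0.5;
- the worst 10% by month 24-30 change are withdrawn after month 30;
- 33 patients for standard errors (66 completers in section 11.5, halved for equal arms).

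**3. One setting worked through (slope SD 0.5, noise SD 0.25).** Let D = Y30 - Y24 and C = Y36 - Y24.

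- D has mean 0.5 and variance 0.5²/4 + 2×0.25² = 0.1875, so SD 0.433. The mean of the top 10% of a normal lies 1.755 SD above the mean: 0.5 + 1.755×0.433 = 1.26.
- Cov(C, D) = 0.5²/2 + 0.25² = 0.1875, so the regression of C on D has slope 1. Mean C in those withdrawn is 1 + 0.76 = 1.76.
- *Month 36 imputed.* The filled change is D/2 = 0.63. Mean C falls by 0.10×(1.76 - 0.63) = 0.113, or 11.3%.
- *Withdrawn patients dropped.* Mean C = (1.00 - 0.176)/0.9 = 0.916, or 8.4% lower.
- *Change-type AUC.* By the trapezoid rule this is D/2 + C/4, mean 0.25 + 0.25 = 0.50. Imputed: 0.113/4 = 0.028, or 5.6% of 0.50. Dropped: withdrawn patients average 0.63 + 0.44 = 1.07, leaving (0.50 - 0.107)/0.9 = 0.437, or 12.7% lower.

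**4. All four settings at 10% removed** (false slowing, confirmed by simulation with 1,000,000 patients per setting):

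| Slope SD / noise SD | Change, imputed | Change, dropped | AUC, imputed | AUC, dropped |
|---|---|---|---|---|
| 0.5 / 0.25 | 11.3% | 8.4% | 5.6% | 12.7% |
| 0.5 / 0.5 | 9.7% | 9.7% | 4.8% | 19.5% |
| 1.0 / 0.25 | 18.2% | 17.9% | 9.1% | 20.9% |
| 1.0 / 0.5 | 15.1% | 16.9% | 7.5% | 25.3% |

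With imputation, the AUC figure is always half the change figure, because month 36 carries weight 1/4 against a mean of 0.50. In standard errors of the open-label mean for 33 patients, the change bias is 0.6-1.1 and the imputed AUC bias about 0.3-0.5. With imputation, removing 5% gives a mean change of 0.90-0.95, and removing 15% gives 0.75-0.86, against a true 1.00.

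**5. False favourable results.** A separate simulation compared the one-year baseline AUC with the one-year idebenone AUC by paired t test (assumed: 0.5 units per year, slope SD 0.5, visit error SD 0.3 or 1.0, n = 33 or 66, 2.5% in the favourable direction, 4000 runs). On a change-type AUC with 10% removed, the rate was 0.034-0.066 with imputation and 0.08-0.19 with those patients left out. With everyone followed to month 36 it was 0.020-0.028.

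**6. Raw-level AUC.** The midpoints of the baseline year and the idebenone year are three years apart, so steady progression alone makes the drug year look worse by 3×0.5 = 1.5 units. Leaving out the worst 20% reduces this only to about 1.2-1.35, and the false favourable rate is 0.000.

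**The case against.** The strongest reply is that item 2 is general discretionary wording in a list introduced as reasons for permanently stopping study drug, and that MS worsening has its own rules with full follow-up. A patient who worsens by two EDSS points or less meets no mandatory EDSS rule and by default stays on drug and in the study; nothing directs removal. This is fair, and it means that the text permits selective loss but does not require it. It does not remove the problem, because item 2 says study rather than treatment, and the narrower reading leads to the two-month limit.

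Other points that stand:

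- Removing exactly the worst 10% is a worst-case selection. The allowance in section 11.5 (85 enrolled for 66 completers, 1 - 66/85 = 22.4%) is all-cause attrition in the parent trial and cannot support a rate of withdrawal for failure here.
- Every patient is on drug, so knowing the treatment adds little, and former placebo patients cannot be targeted while the parent blind holds. The conflicted investigator does not treat or evaluate patients (section 22). Neither fact stops removal of patients who are visibly worsening.
- Section 7.6.1 reports the parent trial as negative and stops the extension for futility, with a final visit and co-enrolment in a natural history study. A misleading efficacy claim is now less likely. The data still go forward for continued analysis, and the text of 9.3 is unchanged.

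A reader might infer that an inert drug would come out looking effective. The documents do not support that as a general statement: it needs a slope or change-type measure and a material share of progressors removed, and with the 11.3(a) imputation the inflation is small to moderate. On a raw-level AUC, a possible reading of 11.2, it fails. Nor do imputation and dropping add up: for a given outcome, a missing month 36 is handled one way or the other, and dropping is the stated rule only for CSF and apheresis.

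**Conclusion.** The conflict is real and should be resolved. As written, 9.3 permits outcome-dependent loss of on-drug data, and on a slope or change-type comparison the bias runs towards idebenone. Its size cannot be determined from the documents. Under the stated assumptions, with the worst 10% removed after month 30, the false slowing is about 5-9% for a change-type AUC with 11.3(a), 8-18% for month 24-36 change, and 13-25% for a change-type AUC with those patients dropped. This is a bias the plan leaves possible; nothing in the documents shows that it occurred.

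**What to change.** Reconcile item 2, items 3 and 4 and the closing paragraph of 9.3 on data collection only.

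- Separate stopping study drug from leaving the study.
- Collect month 30 and month 36 outcomes for every patient who stops drug or is judged a treatment failure. The only exceptions should be withdrawal of consent, loss to follow-up, or a documented safety reason for not attending.
- Include those values in the 11.2 analysis, and state this in section 11.

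No clinical reason for stopping treatment is changed. The cost is protocol wording and at most two already scheduled visits for a few patients. The downside is that some off-drug values enter the idebenone period, as items 3 and 4 already accept.

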10. OUTCOME MEASURES

10.1 Primary outcome measure:

The IPPoMS trial has an adaptive design that will determine the primary outcome measure for the IPPoMS protocol based on pre-determined analysis of the quantitative clinical and neuroimaging secondary outcome measures in the first 30 subjects who finish 1 year of pre-treatment baseline. This analysis is expected to be concluded in the spring/summer of 2013. The primary outcome measure that comes out of the pre-determined analysis in the IPPoMS trial will be adopted as primary outcome measure in the IPPoMS-E trial.

10.2 Secondary outcome measures:

10.2.1 Neuroimaging outcomes:

1. Inhibition of individualized rates of development of brain atrophy: effect of idebenone on individualized rates of development of brain atrophy
2. Inhibition of individualized rates of development of brain gray matter atrophy: effect of idebenone on individualized rates of development of segmented gray matter atrophy
3. Inhibition of individualized rates of enlargement of ventricular volume: effect of idebenone on individualized rates of enlargement of segmented volume of 3rd ventricle
4. Inhibition of individualized rates of development of cervical SC atrophy: effect of idebenone on individualized rates of development of SC atrophy
5. Inhibition of individualized rates of neuroaxonal destruction as assessed by T1 relaxation time in the brain (ROI in normal appearing white matter and in deep gray matter): effect of idebenone on individualized rates of neuroaxonal destruction

6. Inhibition of individualized rates of neuroaxonal destruction as assessed by T1 relaxation time in the cervical spinal cord: effect of idebenone on individualized rates of neuroaxonal destruction
7. Inhibition of individualized changes in axonal integrity as assessed by axial diffusivity and of changes in myelin integrity as assessed by radial diffusivity on brain DTI imaging: effect of idebenone on individualized rates of neuroaxonal destruction

10.2.2 Clinical/functional outcomes:

1. Progression of lower extremity disability as assessed by 25 foot walk component of MSFC (comparing area under curve (AUC) between 1 year of pre-treatment baseline collected during IPPoMS trial and one year of idebenone therapy)
2. Progression of upper extremity/fine motor movements disability as assessed by 9 hole peg test component of MSFC (comparing area under curve (AUC) between 1 year of pre-treatment baseline collected during IPPoMS trial and one year of idebenone therapy)
3. Progression of neurological disability as assessed by MSFC (comparing area under curve (AUC) between 1 year of pre-treatment baseline collected during IPPoMS trial and one year of idebenone therapy)
4. Progression of neurological disability as assessed by Scripps NRS (comparing area under curve (AUC) between 1 year of pre-treatment baseline collected during IPPoMS trial and one year of idebenone therapy)
5. Progression of neurological disability as assessed by EDSS (comparing area under curve (AUC) between 1 year of pre-treatment baseline collected during IPPoMS trial and one year of idebenone therapy)

10.2.3 Biological/immunological outcomes:

1. Analysis of changes in CSF albumin quotient (ROS are known to disrupt endothelial tight junctions; which may be measured as increase in CSF albumin quotient)
2. Analysis of changes in CSF biomarkers of oxidative stress and mitochondrial stress (e.g. 4-HNE, DJ-1)
3. Analysis of changes in CSF lactate, as a biomarker of extra-mitochondrial glucose metabolism
4. Analysis of changes in CSF biomarkers of CNS tissue destruction (e.g. NCAM, OMGP and Contactin-2)
5. Analysis of changes in CSF biomarkers of inflammation (e.g. CXCL13, IL-12p40, sCD27)

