The aim of the present study is extend the data on safety, efficacy and effects on CSF biomarkers of idebenone 2250mg/day (5x150mg tablets three times per day) in patients with PP-MS, over a period of 1 year. Considering the dynamics of improvements in neurological function observed in double blind placebo-controlled trial of idebenone in LHON (*Klopstock, Yu-Wai-Man et al. 2011*) and in FRDA (*Di Prospero, Baker et al. 2007*) we believe that if there was a meaningful therapeutic effect of idebenone in PP-MS, then one year of active therapy would provide sufficient time to observe a difference in the rate of accumulation of neurological disability as compared to the 3 years of natural history from the IPPoMS placebo arm. IPPoMS-E will also provide safety and efficacy data for an additional 1 year in patients randomized to idebenone in IPPoMS.

Furthermore, the IPPoMS-E study will significantly expand the amount of longitudinal CSF biomarker data for idebenone-exposed PP-MS subjects. In patients randomized originally to active drug, IPPoMS-E study will effectively provide three yearly CSF samples on idebenone therapy. Such longitudinal CSF biomarker data on active therapy can be then compared to longitudinal CSF

biomarker data off therapy (i.e. 3 yearly CSF samples in the original placebo arm) for mathematical modeling studies that may provide support for, or contest, a potential neuroprotective effect of idebenone in PP-MS (see section 11: Statistical analysis). Furthermore, the number of paired CSF samples before and after idebenone therapy may theoretically increase up to 100% (if all patients choose to continue in IPPoMS-E protocol), although we consider it likely that some patient will decline participation in IPPoMS-E. This expansion of paired baseline versus treatment CSF samples will effectively provide confirmatory cohort for validation of the changes induced by idebenone treatment that were defined in original IPPoMS trial (see section 11: Statistical analysis).

[figure not shown]

Figure 2: IPPoMS-E trial design

We believe that expansion of efficacy on clinical, imaging and biomarker data may be highly important for supporting or refuting presumed therapeutic equipoise of idebenone and placebo in PP-MS and for selecting the optimal patient population and optimal trial design for the confirmatory trial in case IPPoMS and IPPoMS-E trials indicate therapeutic efficacy.

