5.2 Goals of the study

The primary goals are:

1. To extend long-term (36 months) data on the safety and tolerability of idebenone at 2250 mg/day in patients with PP-MS.
2. To extend CSF biomarker data by significantly expanding (up to 2 fold if all eligible patients proceed to IPPOMS-E) the matched “baseline” vs. “idebenone treatment” CSF samples, which will be analyzed for biomarkers of oxidative stress, mitochondrial function and CNS tissue integrity.
3. To extend efficacy data for idebenone on CNS tissue destruction as measured by quantitative imaging biomarkers and clinical/functional biomarkers in patients previously completing IPPoMS (Protocol Number 09-N-0197). For patients originally randomized to active drug, the idebenone longitudinal data will be extended for total of 3 years, for patients originally randomized to placebo, 3 year pre-treatment or placebo-treatment period will be compared to 1 year idebenone therapy period.

The secondary goals are:

1. To further investigate the mechanism of action of idebenone in PP-MS.
2. To better define biomarkers indicative of therapeutic effect of idebenone on mitochondrial dysfunction and on limiting oxidative damage in PP-MS patients.

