10.3. Tertiary/exploratory outcome measures

10.3.1 Neuroimaging:

1. Progression of Fe accumulation in deep gray matter structures of the brain as assessed by quantification of hypointense signal on T2* MRI imaging
2. Progression of retinal nerve fiber thinning as detected by OCT

10.3.2 Clinical:

1. Progression in cognitive dysfunction as assessed by PASAT component of MSFC (comparing area under curve (AUC) between 1 year of pre-treatment baseline collected during IPPoMS trial and one year of idebenone therapy)
2. Progression in cognitive dysfunction as assessed by Symbol Digit Modality Test (comparing area under curve (AUC) between 1 year of pre-treatment baseline collected during IPPoMS trial and one year of idebenone therapy)
3. Progression of neurological dysfunction as assessed by finger and foot tapping (comparing area under curve (AUC) between 1 year of pre-treatment baseline collected during IPPoMS trial and one year of idebenone therapy)

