11.2 Statistical analyses of outcome measures

Descriptive methods will be used to analyze the safety data. Generally, for the analysis of efficacy data in IPPoMS-E protocol, we will utilize equivalent outcomes collected during IPPoMS trial.

For primary and secondary outcome measures, we will use identical statistical approach as utilized in IPPoMS trial: i.e. in order to utilize all collected data, we will calculate areas under curve (AUC) values for each outcome, normalized per 1 year of “therapy”. Thus, we will calculate AUC for three different “treatments”: pre-treatment baseline (B), placebo (PI) and for idebenone (I) treatment. We will compare intra-individual changes in AUC values by following linear mixed effect model:

$AUC_{\text{outcome}} = \text{treatment (B, PL, I)} + \text{group} + \text{interaction between treatment and group} + \text{covariates}$

where “group” refers to original “placebo” versus “idebenone” groups from IPPoMS trial and the random part is patient. While randomization is stratified for age and therefore, we are expecting that the placebo and active treatment groups will be well-matched for age, we will use Age and sex as covariates in the model if we detect any interaction.

In addition to analysis of primary and secondary outcomes, combining data collected during IPPoMS and IPPoMS-E studies will significantly enhance our ability to detect treatment-related changes in CSF biomarkers. Depending on how many subjects choose to participate in IPPoMS-E, the amount of paired (i.e. no treatment versus idebenone) CSF samples may theoretically increase up to 2 fold in comparison to IPPoMS trial. Therefore, the cohort of patients originally assigned to placebo can be utilized as “confirmatory” cohort for biomarker changes identified in the IPPoMS trial. This would effectively increase the power for detecting significant differences, as only those biomarkers found to be significantly changed during the IPPoMS trial would be tested in the IPPoMS-E trial, thus limiting the number of multiple comparisons that would need to be performed (and for which p values need to be properly adjusted). Again, the differences in selected CSF biomarkers between “no-treatment”, “placebo” and “idebenone” treatment would be analyzed using the same mixed effect model.

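### For patients first given placebo, the efficacy comparison differs between sections in metric and off-drug period, and the AUC model in 11.2 names no principal contrast

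*Combined protocol and SAP*

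**What the plan says.** Four places describe the off-drug comparator for the open-label year.

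- **3.4 Outcome Measures**, for patients originally on placebo: "slopes of disease progression during 2 years of placebo therapy (as measured by primary and secondary outcomes) will be compared to patient-specific slopes" over the open-label year. The metric is slope and the comparator is two placebo years.
- **4.7 Rationale**: a "difference in the rate of accumulation of neurological disability as compared to the 3 years of natural history from the IPPoMS placebo arm". The metric is a rate and the comparator is three years.
- **5.2 Goals**, again for patients originally on placebo: "3 year pre-treatment or placebo-treatment period will be compared to 1 year idebenone therapy period". No metric is given.
- **10.2.2 Clinical/functional outcomes**, all five items and not restricted by original arm: "comparing area under curve (AUC) between 1 year of pre-treatment baseline collected during IPPoMS trial and one year of idebenone therapy". The metric is AUC and the comparator is the single pre-treatment year. Section 10.3.2 repeats the wording for the tertiary clinical outcomes.

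Section 11.2 then gives the analysis: "in order to utilize all collected data, we will calculate areas under curve (AUC) values for each outcome, normalized per 1 year of" therapy. AUC is computed separately for pre-treatment baseline, placebo and idebenone. It enters a mixed model with treatment, original group, their interaction and covariates, and patient as the random part. The section does not state which contrast answers the efficacy question. For the method it points to the parent trial: "For primary and secondary outcome measures, we will use identical statistical approach as utilized in IPPoMS trial".

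**The concern.** A reader who wants the within-patient effect of switching from placebo to idebenone finds two metrics (slope and AUC) and three off-drug periods (one, two and three years). The model in 11.2 does not choose between them.

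The choice matters because the disease is progressive and the idebenone year always comes last. A summary that depends on calendar position, or on the length of the period, will differ between periods even if the drug does nothing. Dividing AUC by the number of years does not remove this when the periods last 1, 2 and 1 years and the model has no time term. Natural progression could then be read as harm or as benefit, depending on a definition these documents do not give.

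**Working it through.** The plan states no figure for this comparison, and 11.4 gives no power calculation, so there is nothing to reproduce. The check asks what each contrast is expected to equal when the drug has no effect.

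**Inputs.** Periods for a patient originally on placebo: baseline 1 year, placebo 2 years, open label 1 year (3.4, 10.2.2). Clinical data are 6-monthly (11.3). The month 24 assessment of IPPoMS is the extension baseline (7.4). Assumed: visits at months -12, -6, 0, and so on to 36; linear worsening of s per year, with scores oriented so that higher is worse. The documents give no value of s, so results are in multiples of it.

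**Does the model choose the contrast?** With baseline (B), placebo (P) and idebenone (I) crossed with two groups, there are six fixed parameters before covariates. Only five period-by-group cells exist, because the original idebenone group has no placebo period. In the original placebo group, I - B, I - P and I - (B + 2P)/3 are all estimable. The model leaves the choice open.

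**Raw-score AUC per year** is s times the mean time of the period in years: B = -0.5s, P = 1.0s, I = 2.5s. B and P weighted by length give (-0.5 + 2 × 1.0)/3 = 0.5s.

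**Change-from-start AUC divided by period length L** is sL/2: B = 0.5s, P = 1.0s, I = 0.5s. B and P weighted by length give (0.5 + 2 × 1.0)/3 = 0.83s.

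**Slope** is s in every period. **Change-from-start AUC over 12-month windows** is 0.5s in every window.

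| No-effect contrast | Raw AUC | Change AUC ÷ length | Slope | 12-month windows |
|---|---|---|---|---|
| I - B | 2.5 - (-0.5) = +3.0s | 0.5 - 0.5 = 0 | 0 | 0 |
| I - P | 2.5 - 1.0 = +1.5s | 0.5 - 1.0 = -0.5s | 0 | 0 |
| I - B and P by length | 2.5 - 0.5 = +2.0s | 0.5 - 0.83 = -0.33s | 0 | 0 |

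On raw AUC an inert drug looks harmful against every comparator. On change-from-start AUC it looks beneficial against any comparator that includes the placebo years.

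**Precision of the slope contrast**, with independent errors of equal variance σ² and month 24 shared by adjoining periods. The variance is 4.0σ² against the pre-treatment year, 3.2σ² against the placebo years and 2.57σ² against all off-drug follow-up. The standard error with all off-drug follow-up is therefore √(2.57/4.0) = 0.80 of that with the pre-treatment year (20% smaller), and √(2.57/3.2) = 0.90 of that with the placebo years (10% smaller).

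**If worsening accelerates**, with the yearly rate rising by a each year, a period's slope is a times its mean time. The no-effect slope contrast becomes 2.5 - (-0.5) = +3.0a (pre-treatment year), 2.5 - 1.0 = +1.5a (placebo years) or 2.5 - 0.5 = +2.0a (all off-drug).

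**The case against.** Several points on the other side stand.

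- The AUC definition may sit in the parent protocol, to which 11.2 refers. The supportable statement is that these documents do not define it, not that it is undefined. The parent plan is less likely to define the placebo-to-idebenone contrast, because that switch happens only in the extension.
- A reader might infer that 10.2.2 is itself biased. The documents do not support that. It is a whole-cohort comparison, and the pre-treatment year is the only off-drug period both original arms share. Its items are titled as progression, which suggests change, and on that reading its no-effect value is 0.
- A reader might also infer a bias of -1.0s against the three off-drug years (0.5s - 1.5s). That needs one AUC over a merged three-year period, which 11.2 never computes. Its own baseline and placebo terms give -0.33s.
- Section 4.7 can be read as a reference to a group, and the wording of 5.2 is ambiguous. The difference between 3.4 and both 10.2.2 and 11.2 does not depend on either.
- Section 11.2 does specify a slope test that pools baseline and placebo, but for CSF biomarkers. The samples it lists omit the open-label sample of patients originally on placebo, so it does not fill the gap.
- The study was stopped for futility after the parent trial showed no efficacy (7.6.1), and it never had a powered test. This limits the consequence but does not resolve the inconsistency.

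**Conclusion.** The point holds for patients originally on placebo. Metric and off-drug period differ between 3.4, 5.2 and 10.2.2, and 11.2 names no principal contrast. With no drug effect, the idebenone-minus-placebo contrast in 11.2 is off by +1.5s or -0.5s, so it is biased on either reading of AUC. Idebenone minus baseline is off by +3.0s on raw AUC and by nothing on change-from-start AUC. These sizes assume linear worsening and 6-monthly visits; the conflict in the text assumes neither.

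The documents do not support a claim that a confirmatory result is compromised. What is affected is the reading of an uncontrolled extension whose data, under 7.6.1, move to another protocol for continued analysis. The correction is worth making on that ground.

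**What to change.** Reconcile 3.4, 5.2, 10.2.2 and 11.2, and align 10.3.2. For the within-patient comparison in patients originally on placebo, use slope, as 3.4 already states, or change-from-start AUC over equal 12-month windows. Write that definition into 11.2 and name one principal contrast.

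Either off-drug comparator is acceptable. All off-drug follow-up (5.2) is more precise. The placebo years (3.4) drift less if progression accelerates (+1.5a against +2.0a). Keep the pre-treatment-year comparison for the whole cohort or as a sensitivity analysis.

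The cost is wording and a minor reanalysis, with no new data. Three limits should be stated:

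- The choice is now post hoc and should be labelled so.
- The method assumes a roughly linear off-drug course.
- On-drug slopes rest on months 24, 30 and 36, so confidence intervals should be shown. Early stopping may leave some patients without month 36. If that visit is filled by the 11.3 rule ("we will substitute the data for this time-point by the average of 2 preceding time-points"), then with month 24 set to 0 and month 30 at 0.5s it becomes 0.25s. The no-effect slope is then 0.25s instead of s, so the zero in the table needs an observed month 36.
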